10.5.9 Analysis of safety & tolerability

The number and percentage of patients withdrawing from trial treatment due to toxicity or experiencing delay to scheduled surgery/neoadjuvant chemotherapy/endocrine therapy will be tabulated, as will the number and percentage of patients reporting a Serious Adverse Event (SAE) and Grade 3 or higher toxicity (summarised by treatment, overall and by NCI-CTCAE short term). Comparisons between treatment arms will be by an exact test.

Further details of the statistical analyses (dummy tables and graphs) will be included in a formal Statistical Analysis Plan, to be signed off before patient recruitment begins.

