9 TRIAL TREATMENT

9.1 Introduction

Patients will be randomised 3:1 to 9mg of enobosarm (therapeutic arm) to a control arm receiving “treatment as usual” with no placebo. Enobosarm will be taken orally, once daily, up to surgery/neoadjuvant chemotherapy/endocrine therapy which should take place 14 days +4 days from commencing treatment. Enobosarm will be prescribed in hospital and is self-administered at home by the patients. Patients will be dispensed two bottles containing 35 enobosarm softgels (enough in each for a 7 day course +4 days/wastage) at Visit 1 (Baseline). Compliance to treatment will be checked through a patient drug diary on Day 14 (Visit 2) hospital visit. Remaining unused enobosarm will be collected and accounted for at Visit 2.

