10 STATISTICAL CONSIDERATIONS

10.1 Method of Randomisation

The sequence of allocations will be centrally generated by the LCTC study statistician using the Stata package *ralloc* employing permuted block randomisation with variable block length, and 3:1 (enobosarm : control) allocation to the two treatment arms.

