10.2.3 Safety Endpoints

- Occurrence of grade 3+ toxicity as classified by NCI-CTCAE v 4.03
- Occurrence of serious adverse events
- Withdrawal from trial treatment due to toxicity
- Experience of delay to scheduled surgery/neoadjuvant chemotherapy or endocrine therapy

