10.3 Sample Size

In the absence of a clearly defined or a clinically relevant difference for Ki67, the primary efficacy parameter will be the probability that the response in one group will be “better” than the response in the other group. This may be referred to as the Probability of Benefit or PoB, and is directly estimated by the (scaled) Mann-Whitney statistic; in the present context a “good” response is a greater reduction in the Ki67 index in the treated arm, and a useful reduction in Ki67 is taken to be a PoB of 0.67 (odds of 2:1 favouring the intervention, and equivalent to a standardised effect size of 0.62).

To demonstrate a PoB (in terms of a reduced Ki67 index) of 0.67, with 5% two-sided significance and 90% power we require 147 patients (with allocation 3:1 enobosarm: “treatment as usual” control). This can be achieved from a minimum of 7 sites assuming an average of 2 pts/site/month and 2 sites opened/month (actually yielding 150 patients), with duration of accrual of 14 months.

The recruitment rate/site estimate is based on the recruitment to the POETIC study (Smith et al. 2011) from the selected centres. Based on previous studies loss to follow-up is expected to be minimal (<1%) as this is a highly motivated group of participants, follow-up is brief and assessment non-invasive.

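### Stopping trial treatment for toxicity is put to a between-arm exact test, although control patients have no trial treatment to stop

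*Protocol*

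**What the plan says.** Section 10.2.3 of the protocol names four safety endpoints, one of which is "Withdrawal from trial treatment due to toxicity". Section 10.5.9 starts with it: "The number and percentage of patients withdrawing from trial treatment due to toxicity". That section then adds delay to planned surgery or neoadjuvant therapy, SAEs, and grade 3 or higher toxicity, and follows with a single general sentence: "Comparisons between treatment arms will be by an exact test". No item is excepted.

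Three other places bear on the point:

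- Section 9.1 describes the control arm as usual care "with no placebo. Enobosarm will be taken orally, once daily". Section 7.6.1 asks only patients allocated to enobosarm to keep a drug diary.
- Section 10.5.1 defines the safety set as all patients, so controls enter any between-arm safety comparison.
- Section 10.5.7 sets every significance level other than the primary one at 5% two-sided, and says summary statistics will carry 95% confidence intervals.

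**The concern.** A control patient cannot stop a treatment that was never given. The control result of zero is fixed by the design and is not an observation. Fisher's exact test nevertheless treats 0 of about 37 as a sample from an unknown rate and asks whether that rate equals the rate on enobosarm. The true control rate is known to be zero, so a single withdrawal on enobosarm already shows that the rates differ. The p-value then reflects mainly the arm sizes and the 3:1 split.

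At stake is how one tolerability endpoint is read. Safety and tolerability is a stated secondary objective (section 2.3.2). A non-significant p-value printed beside this row could be taken to mean that enobosarm is tolerated like no treatment, when the comparison cannot answer that question.

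**Working it through.** **Inputs**

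- Total sample size (section 10.3): "with 5% two-sided significance and 90% power we require 147 patients".
- Allocation (section 10.1): "3:1 (enobosarm : control) allocation to the two treatment arms".
- Test level: 5% two-sided (section 10.5.7).
- Control count: 0, from the no-placebo design (section 9.1).
- True withdrawal rate on enobosarm: not stated in the protocol. A range from 5% to 15% is assumed below.

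**Step 1. The plan's own figure and the arm sizes.** Section 10.3 sets the target effect: "a useful reduction in Ki67 is taken to be a PoB of 0.67". For normal data this corresponds to a standardised difference of √2 × z(0.67) = 0.622, against the stated 0.62. The two-sample formula for means gives controls = (1 + 1/3) × [(1.960 + 1.282)/0.62]² = 36.4, and a total of 4 × 36.4 = 145.8. Power at 147 is 90.2%. So 147 is reproduced to within two patients by this formula. A rank-based formula (Noether) gives 161.6, but the present point needs only the arm sizes: 147 × 3/4 = 110.25 and 147 × 1/4 = 36.75, taken as 110 v 37.

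**Step 2. The exact test against a fixed zero.** With k withdrawals, all necessarily on enobosarm, the one-sided Fisher probability is C(110, k)/C(147, k). For k = 5 it is 0.229: under equal rates and 3:1 allocation, all five events would fall in the larger arm nearly a quarter of the time. The two-sided p-value adds the tables that are no more probable:

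| Withdrawals on enobosarm | Observed rate | Two-sided p v 0/37 |
|---|---|---|
| 5/110 | 4.5% | 0.331 |
| 8/110 | 7.3% | 0.202 |
| 10/110 | 9.1% | 0.066 |
| 11/110 | 10.0% | 0.066 |
| 12/110 | 10.9% | 0.038 |

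No count up to 11 reaches p < 0.05; the threshold is 12. With a split of 111 v 36 the threshold is again 12 (10.8%), and 11/111 gives p = 0.066.

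**Step 3. How often the test would be significant.** This is P(X ≥ 12) for X ~ Binomial(110, r):

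| Assumed true rate r | Chance of p < 0.05 |
|---|---|
| 5% | 0.9% |
| 8% | 17% |
| 10% | 42% |
| 12% | 68% |
| 15% | 91% |

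**Step 4. The one-arm description instead.** The exact (Clopper-Pearson) 95% limits are the 2.5% quantile of Beta(k, 110 − k + 1) and the 97.5% quantile of Beta(k + 1, 110 − k):

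- 0/110: 0% (0% to 3.3%)
- 5/110: 4.5% (1.5% to 10.3%)
- 11/110: 10.0% (5.1% to 17.2%)

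These intervals state what the trial can say about stopping for toxicity, without a comparison that the design does not support.

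**The case against.** The strongest reply is that section 10.5.9 does not clearly commit to this test. Withdrawals and delays are to be tabulated, and the closing sentence may only name the method for whatever is compared. Which rows carry a p-value could be settled in the analysis plan, which is not at hand. This has some force. But the sentence follows a list that begins with this endpoint, and nothing limits its reach. The natural reading includes it, and the protocol itself should not leave that open.

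The second reply is that most of the remedy is already planned. Number and percentage are required by section 10.5.9, and section 10.5.7 promises 95% intervals for summary statistics. That stands, and it lowers the weight of the point. What remains is a p-value with no useful meaning beside an informative estimate.

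Stronger readings are tempting, and the documents do not support them:

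- A reader might infer that about 10% of enobosarm patients are expected to stop. The protocol gives no expected rate. Ten per cent is only the largest observed rate that stays non-significant. The background in section 2.1, though indirect, does not point to it: at 9 mg, 95% of recorded adverse events were grade 1 or 2.
- A reader might infer that every such withdrawal is caused by enobosarm. Only treated patients can stop, but the event behind the stop may be unrelated; section 11.5 provides a causality scale for that.
- A reader might infer that the trial's verdict on tolerability rests on this row. Section 4.3 lists five safety and tolerability measures, including all adverse events of all grades. There is no efficacy or futility stopping rule, and section 10.4 treats the interim review as guidance only.
- A reader might infer that the plan will declare equal tolerability from a non-significant test. No section says so.

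**Conclusion.** The point holds as a minor error in the analysis as written. One named safety endpoint is a structural zero in the control arm, and the exact test applied to it has no meaningful null hypothesis. With 110 v 37, up to 11 observed withdrawals (10.0%) would give p > 0.05. At assumed true rates of 5% and 10%, the test is significant in about 1% and 42% of trials. A significant result would add nothing to the one-arm proportion.

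This rests on full recruitment at 3:1, on a two-sided Fisher test as the exact test meant, and on reading the general sentence in section 10.5.9 as covering every item listed before it. The rates are illustrations only. The primary analysis is unaffected, and so is the exact test for SAEs, grade 3 or higher toxicity, and delay to surgery or neoadjuvant therapy.

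**What to change.** In section 10.5.9, state that stopping trial treatment because of toxicity will be reported descriptively for the enobosarm arm only, as number, percentage and exact 95% confidence interval. State also that the exact test between arms applies only to endpoints that can occur in both arms: SAEs, grade 3 or higher toxicity, and delay to surgery or neoadjuvant therapy. The enobosarm patients in the existing safety set can serve as the denominator, so no new analysis population is needed.

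The cost is one or two sentences in the protocol, carried into the analysis plan. No data collection, visits or patient numbers change.

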11 PHARMACOVIGILANCE

11.1 Terms and Definitions

The following definitions have been adapted from European Directive 2001/20/EC and ICH GCP E6

Adverse Event (AE)

Any untoward medical occurrence [i.e. any unfavourable or unintended sign (including abnormal laboratory results), symptom or disease] in a research patient to whom a medicinal product has been administered, including occurrences which are not necessarily caused by or related to that product.

Adverse Reaction (AR)

Any untoward and unintended response in a patient to an investigational medicinal product which is related to any dose administered to that patient.

Unexpected Adverse Reaction (UAR)

An adverse reaction the nature and severity of which is not consistent with the information about the medicinal product in question set out in the IB relating to the trial in question.

Serious Adverse Event (SAE) or Serious Adverse Reaction (SAR)

Any adverse event or adverse reaction is classified as serious if it:

- a) results in death
- b) is life-threatening* (patient at immediate risk of death)
- c) requires in-patient hospitalisation or prolongation of existing hospitalisation**
- d) results in persistent or significant disability or incapacity, or
- e) consists of a congenital anomaly or birth defect

Suspected Unexpected Serious Adverse Reaction (SUSAR)

A serious adverse reaction that is 'unexpected' (the nature and severity of which IS NOT consistent with the IB (see expected classifications)) is termed as a suspected unexpected serious adverse reaction.

*'life-threatening' in the definition of 'serious' refers to an event in which the patient was at risk of death at the time of the event; it does not refer to an event which hypothetically might have caused death if it were more severe.

[figure not shown]
**Hospitalisation is defined as an inpatient admission, regardless of length of stay, even if the hospitalisation is a precautionary measure for continued observation. Hospitalisations for a pre-existing condition, including elective procedures that have not worsened, do not constitute an SAE.

11.2 Time Period for Safety Reporting

Safety reporting of Serious Adverse Events or Reactions will be reported during the clinical trial from the period of randomisation until Day 21 - 28 Follow-up Visit.

Investigators are expected to report any SAE that ‘they become aware of’ and feel is related to trial treatment after the reporting time period stated in the protocol.

11.2.1 Flowchart for Reporting Requirements of Adverse Events

**If an adverse event occurs outside of this time window and the local investigator feels that the event is related to the trial treatment administered, the above process should still be followed.*

11.3 Notes on Adverse Event Inclusions and Exclusions

11.3.1 Include

- An exacerbation of a pre-existing illness
- An increase in frequency or intensity of a pre-existing episodic event/condition
- A condition (even though it may have been present prior to the start of the trial) detected after trial drug administration
- Continuous persistent disease or symptoms present at baseline that worsens following the administration of the study/trial treatment
- Laboratory anomalies that require clinical intervention or further investigation (unless they are associated with an already reported clinical event)
- Abnormalities in physiological testing or physical examination that require further investigation or clinical intervention
- Injury or accidents
- Changes in libido

11.3.3 Notes on Adverse Events Relating to Change in Libido

Patients should be asked at each visit if they have had a change in libido since baseline. Changes in libido were recorded in mouse model trials of enobosarm but there is no data to support this in humans. Changes in libido should be recorded according to the NCI-CTCAE Version 4.03, however the grading system for this event may not apply to all patients so instead a grading of 1 – mild, 2 – moderate, 3 – high should be used based on the patients answers.

11.3.4 Notes on Adverse Events Relating to Neoadjuvant Chemotherapy or Endocrine Therapy

Any adverse events or serious adverse events relating to neoadjuvant chemotherapy or endocrine therapy should NOT be reported to the LCTC, unless there is suspicion that these may also be related to enobosarm or the research core biopsy. If the AE is not possibly, probably or highly probably related to the chemotherapy or endocrine therapy drug then the adverse event should be reported to the LCTC. If the relationship to chemotherapy, endocrine therapy, enobosarm or the research core biopsy is unclear the AE/SAE should be reported.

11.4 Notes Severity/Grading of Adverse Events

Regardless of the classification of an AE as serious or not, its severity must be assessed according to medical criteria alone.

The assignment of the severity/grading should be made by the investigator responsible for the care of the patient using the NCI-CTCAE Version 4.03.

If the AE/SAE is not covered by the NCI-CTCAE then the investigator should use the definitions below.

Mild: does not interfere with routine activities

Moderate: interferes with routine activities

Severe: impossible to perform routine activities

Life threatening

Death

A distinction is drawn between serious and severe AEs. Severity is a measure of intensity (see above) whereas seriousness is defined using the criteria in section 11.1, hence, a severe AE need not necessarily be a Serious Adverse Event.

11.5 Relationship to Trial Treatment

The assignment of the causality should be made by the investigator responsible for the care of the participant using the definitions in Table 4.

If any doubt about the causality exists the local investigator should inform the study coordination centre who will notify the Chief Investigators. In the case of discrepant views on causality between the investigator and others, the MHRA will be informed of both points of view.

Table 4: Definitions of Causality

Relationship	Description
None	There is no evidence of any causal relationship. N.B. An alternative cause for the AE should be given
Unlikely	There is little evidence to suggest there is a causal relationship (e.g. the event did not occur within a reasonable time after administration of the trial medication). There is another reasonable explanation for the event (e.g. the patient's clinical condition, other concomitant treatment).
Possibly	There is some evidence to suggest a causal relationship (e.g. because the event occurs within a reasonable time after administration of the trial medication). However, the influence of other factors may have contributed to the event (e.g. the patient's clinical condition, other concomitant treatments).
Probably	There is evidence to suggest a causal relationship and the influence of other factors is unlikely.
Highly Probable	There is clear evidence to suggest a causal relationship and other possible contributing factors can be ruled out.

11.6 Expectedness

An AE whose causal relationship to the study drug is assessed by the investigator as “possible”, “probable”, or “highly probable” is an Adverse Drug Reaction.

All events judged by the investigator to be possibly, probably, or highly probably related to the IMP, graded as serious and **unexpected** should be reported as a SUSAR. In accordance with the Reference Safety Information (See Section 11.7) there are no expected serious adverse reactions, therefore all events that are deemed related and serious must be reported as SUSARs.

11.7 Reference Safety Information

The Reference Safety Information (RSI) for the IMP used in this trial is as follows:

Enobosarm (GTx – 024) – Investigator Brochure – Section 8.1, Appendix A

GTx-024 is the pharmaceutical company (GTx Inc.) reference name for enobosarm, the brand name is Ostarine.

The current version RSI documents applicable to the trial for the current reporting period are available on the LCTC portal (www.lctu.org.uk).

11.8 Follow-up After Adverse Events

All adverse events should be followed until satisfactory resolution or until the investigator responsible for the care of the patient deems the event to be chronic or the patient to be stable.

When reporting SAEs and SUSARs the investigator responsible for the care of the patient should apply the following criteria to provide information relating to event outcomes: resolved; resolved with sequelae (specifying with additional narrative); not resolved/ongoing; ongoing at final follow-up; fatal or unknown.

11.9 Reporting Procedures

All adverse events should be reported from the point of consent until 21 -28 days post treatment, depending on the patient’s scheduled follow-up visit. Depending on the nature of the event the reporting procedures below should be followed. Any questions concerning adverse event reporting should be directed to the LCTC in the first instance.

11.9.1 Non serious ARs/AEs

All such events, whether expected or not, should be recorded on the AE Form and sent to the LCTC via post, email or fax within 30 days of completion of the follow-up visit.

11.9.2 Serious ARs/AEs/SUSARs

SARs, SAEs and SUSARs should be reported within 24 hours of the local site becoming aware of the event via email or fax using the SAE Form, either method should be accompanied by a

phone call. The SAE Form asks for the nature of event, date of onset, severity, corrective therapies given/whether treatment was stopped, outcome and causality. The responsible investigator should sign the causality of the event. Additional information should be sent within 5 days if the reaction has not resolved at the time of reporting.

The LCTC will notify the MHRA and REC of all SUSARs occurring during the study according to the following timelines; fatal and life-threatening within 7 days of notification and non-life threatening within 15 days. All investigators will be informed of all SUSARs occurring throughout the study. Local investigators should report any SUSARs and/or SAEs as required by their R&D Office.

11.10 Responsibilities – Investigator

The investigator is responsible for reporting all AEs that are observed or reported during the study, regardless of their relationship to study product.

All SAEs must be reported immediately by the investigator to the LCTC on an SAE form (available on the LCTC Portal) unless the SAE is specified in the protocol or IB as not requiring immediate reporting. All other adverse events should be reported on the Adverse Events Form.

Minimum information required for reporting:

- Study identifier
 - Study centre
 - Patient number
 - A description of the event
 - Date of onset
 - Current status
 - Whether study treatment was discontinued
 - The reason why the event is classified as serious
 - Investigator assessment of the association between the event and study treatment
- i. The SAE form should be completed by the responsible investigator i.e. the consultant named on the 'signature list and delegation of responsibilities log' who is responsible for the patient's care. The investigator should assess the SAE for the likelihood that it is a response to an investigational medicine. In the absence of the responsible investigator the form should be completed and signed by a designated member of the site trial team and faxed to the LCTC immediately. The responsible investigator should check the SAE form, make changes as appropriate, sign and then re-fax to the LCTC as soon as possible. The initial report shall be followed by detailed, written reports.
- ii. Send the SAE form by fax (within 24 hours or next working day) to the LCTC

[contact]

If no fax machine is available then the SAE form should be uploaded to the LCTC Portal and the Trial Coordinator informed by telephone. This process is detailed in the work instruction Transferring Files via the LCTC Portal.

- iii. The responsible investigator must **notify** their R&D department of the event (as per standard local procedure).
- iv. In the case of an SAE the patient must be followed-up until clinical recovery is complete and laboratory results have returned to normal, or until the event has stabilised. Follow-up may continue after completion of protocol treatment if necessary.
- v. Follow-up information is noted on another SAE form by ticking the box marked 'follow-up' and faxing to the LCTC as information becomes available. Extra, annotated information and/or copies of test results may be provided separately.
- vi. The patient **must** be identified by trial number, date of birth and initials only. The patient's name **should not** be used on any correspondence.

11.11 Responsibilities – CRUK LCTC

The LCTC is undertaking duties delegated by the trial sponsor, University of Liverpool, and is responsible for the reporting of SUSARs and other SARs to the regulatory authorities (MHRA, competent authorities of other European member states in which the trial is taking place and, if required, the REC) as follows:

- SUSARs which are fatal or life-threatening must be reported not later than 7 days after the LCTC is first aware of the reaction. Any additional relevant information must be reported within a further 8 days.
- SUSARs that are not fatal or life-threatening must be reported within 15 days of the LCTC first becoming aware of the reaction.
- A list of all SARs (expected and unexpected) must be reported annually.

It is recommended that the following safety issues should also be reported in an expedited fashion:

- An increase in the rate of occurrence or a qualitative change of an expected serious adverse reaction, which is judged to be clinically important
- Post-study SUSARs that occur after the patient has completed a clinical trial and are notified by the investigator to the sponsor
- New events related to the conduct of the trial or the development of the IMPs and likely to affect the safety of the patients, such as:
 - a. A serious adverse event which could be associated with the trial procedures and which could modify the conduct of the trial
 - b. A significant hazard to the patient population, such as lack of efficacy of an IMP used for the treatment of a life-threatening disease
 - c. A major safety finding from a newly completed animal study (such as carcinogenicity)
 - d. Any anticipated end or temporary halt of a trial for safety reasons and conducted with the same IMP in another country by the same sponsor
- Recommendations of the Data Monitoring Committee, if any, where relevant for the safety of the patients

Staff at the LCTC will liaise with the designated Clinical Co-ordinator who will evaluate all SAEs received for seriousness, expectedness and causality. Investigator reports of suspected SARs will be reviewed immediately and those that are SUSARs identified and reported to regulatory authorities and REC. The causality assessment given by the Local Investigator at the hospital cannot be overruled and in the case of disagreement, both opinions will be provided with the report.

The LCTC will also send an annual safety report containing a list of all SARs to regulatory authority and REC.

All SAEs and SARs will be reported to GTx, Inc. via CMED upon resolution. SUSARs and all follow-up information will be reported to GTx, Inc. and CMED concurrently to reports made to the competent authority as above (within 7 days for SUSARs which are fatal or life-threatening and within 15 days for SUSARs that are not fatal or life-threatening). Any additional information will be provided within 7 days of receipt at the LCTC. Furthermore a full list of AEs will be provided annually. Reports to CMED will be automatically generated via the MACRO Pharmacovigilance database.

Patient safety incidents that take place in the course of research should be reported to the National Patient Safety Agency (NPSA) by each participating NHS Trust in accordance with local reporting procedures.

